**Table 5-1: NBI International Colorectal Endoscopic (NICE) Classification**

NICE Classification	Type 1	Type 2
Color	Same or lighter than background	Browner relative to background (verify color arises from vessels)
Vessels	None, or isolated lacy vessels may be present coursing across the lesion	Brown vessels surrounding white structures
Surface Pattern	Dark or white spots of uniform size, or homogeneous absence of pattern	Oval, tubular or branched white structures surrounded by brown vessels
Predicted Histology (Human or CDSD)	Non-Adenoma	Adenoma

After making their prediction using NBI alone, the endoscopist or coordinator will enable PiP to allow the endoscopist to observe the CDSD result. The CDSD result shall be recorded as 1) Adenoma, 2) Non-adenoma, or 3) No prediction after system stabilization. The endoscopist considers their initial prediction and the output of the device to make a final combined prediction of polyp histology as ‘Adenoma’ or ‘Non-adenoma’. The endoscopist will make a determination of their confidence in their prediction as either ‘high’ or ‘low’. If CDSD does not return a prediction this does not indicate that no polyp is present. More likely, this output is due to the module not being able to make a clear adenoma/non-adenoma assessment based on the training the model has received. Based on software validation testing, this is expected to occur in approximately 11-16% of the polyps. In cases that this occurs, the result will be recorded as “no prediction”. In this scenario, the endoscopist will make a final prediction without the aid of CDSD.

Polyps will be biopsied or resected as per the standard of care and placed in a separate specimen jar or polyp trap chamber and uniquely labeled as per standard procedure. The exam will continue and the steps above are repeated for each identified diminutive lesion. At the end of the procedure, polyp specimens are sent to pathology for review. The pathologist is blinded to the endoscopist predictions and CDSD prediction.

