The diagnosis will be rendered by the pathologist, who is blinded to the endoscopists' polyp characterization, and the pathology report will be reviewed by the endoscopist. A CDSD-aided or CDSD-unaided prediction of Adenoma will be rendered as a True Positive when the pathological diagnosis is 'conventional adenoma' (a.k.a. tubular adenoma), tubulovillous adenoma, villous adenoma, traditional serrated adenoma (TSA), adenoma with high grade dysplasia or cancer. A CDSD-aided or unaided prediction of non-adenoma will be rendered as a True Negative when the pathological diagnosis is hyperplastic polyp, sessile serrated polyp (SSP), inflammatory polyp, lymphoid aggregate/follicle, granulation tissue or normal colonic mucosa. Diminutive polyps that are lost following resection or destroyed during pathology prior to diagnosis will be excluded from the analysis due to lack of ground truth pathology results.

In cases where the CDSD-aided endoscopist prediction and the pathology result differs, a recut and reanalysis of the tissue block will be conducted. In such cases, the second successful pathology reading will be recorded and used as the histopathological ground truth.

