### 5.2 *Treatment Assignment*

For each participating endoscopist, consecutive subjects presenting for colonoscopy and meeting the pre-procedure entrance criteria will be consented and screened. Subjects meeting all the entrance criteria will be enrolled and undergo colonoscopy according to the standard of care with the added use of CDSD.

During the procedure, subjects found to meet any of the exclusion criteria will be excluded from the study. CDSD will be applied to all endoscopist-identified diminutive polyps in all subjects. Pathology will be blinded to all predictions. See Figure 5-1 for details.

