### 8.5 Post-Procedure

Lab results will be collected for all specimens sent to pathology, including secondary lab results in cases where a recut/re-analysis of specimen is requested by the endoscopist and

performed. Diagnosis based on pathology will be recorded as well as prescribed surveillance interval.

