#### 9.1.1.3 Statistical Methods

The 95% confidence intervals for the differences between CDSD-aided and CDSD-unaided sensitivity and specificity are estimated using bootstrap resampling with resampling performed first at the endoscopist level and then at the patient level. The null hypothesis is rejected if both lower bounds of the confidence intervals are greater than 0.

$$Sn_{CDSD\text{-aided}} - Sn_{CDSD\text{-unaided}} > 0$$

$$Sp_{CDSD\text{-aided}} - Sp_{CDSD\text{-unaided}} > 0$$

The assumptions of the statistical model used to establish the sample size are:

1. There are at a minimum 40 endoscopists participating in the study and each endoscopist makes approximately 60 predictions,
2. For each endoscope (CF-HQ190 and PCF-H190) and for each class of diminutive polyp (adenoma and non-adenoma) there is an intra-cluster correlation coefficient of 0.05 for predictions made by the same endoscopist,
3. There is no correlation between an operator's sensitivity and specificity,
4. There is no correlation between predictions made by the same operator across endoscope models (CF-HQ190 and PCF-H190),
5. The distribution of adenomas and non-adenomas within subjects with more than one diminutive polyp was modelled and is described in the statistical analysis plan,
6. The values from the range of possible values for the discordant pairs (b, c, n and p) that are used to calculate sample size are reported in Tables 9-3, 9-4, 9-5 and 9-6),
7. Without CDSD, the operator sensitivity is presumed to be 88% and the specificity is presumed to be 58% across all operators for all colonoscopes. The operator sensitivity with CDSD is presumed to be 92% and specificity with CDSD is presumed to be 75% across all operators when using the CF-HQ190 colonoscope (benchtop testing data). The operator sensitivity with CDSD is presumed to be 91% and the specificity with CDSD is presumed to be 72% across all operators when using the PCF-H190 colonoscope (benchtop testing data). Combined, the operator

sensitivity with CDSD is presumed to be 92% and the specificity with CDSD is presumed to be 73% across all operators,

8. The prediction rate for CDSD with CF-HQ190 is 89% and the prediction rate for CDSD with the PCF-H190 is 84% (benchtop testing data),
9. The proportion of subjects examined with the PCF-H190 will be 50%,

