10. The proportion of subjects that present with adequate bowel preparation will be 85%, the proportion of patients with diminutive polyps will be 52%, there will be 1.81 diminutive polyps per subject having diminutive polyps, the overall prevalence of adenomas will be 58%,
11. The proportion of predictions with and without CDSD that will be assessed as normal tissue by pathology is estimated to be approximately 15%.

A simulation analysis was performed in which a dataset is generated at each step following the assumptions above. To account for intra-cluster correlation at the endoscopist level, for each endoscope and each class of diminutive polyps, the proportions of accurate and non-accurate predictions are sampled following a Dirichlet distribution, as described in Gönen. At each simulation step, bootstrap resampling based 95% confidence intervals for the differences between CDSD-aided and CDSD-unaided sensitivity and specificity are calculated. Bootstrap resampling is performed first at the endoscopist level and then at the patient level. The power is calculated as the number of simulation steps where the lower bound of both confidence intervals is greater than 0.

**Table 9-3: Assumptions for Proportions of Predictions for Adenomas (Sensitivity, Reference Standard Positive) with CF-HQ190**

		CDSD-unaided Prediction		Total
		Positive	Negative	
CDSD-aided Prediction	Positive	0.8411	0.0859	0.9270
	Negative	0.0365	0.0365	0.073
	Total	0.8776	0.1224	1.00

**Table 9-4: Assumptions for Proportions of Predictions for Adenomas (Sensitivity, Reference Standard Positive) with PCF-H190**

		CDSD-unaided Prediction		Total
		Positive	Negative	
CDSD-aided Prediction	Positive	0.8301	0.0749	0.905
	Negative	0.0475	0.0475	0.095
	Total	0.8776	0.1224	1.00

**Table 9-5: Assumptions for Proportions of Predictions for Non-Adenomas (Specificity, Reference Standard Negative) with CF-HQ190**

		CDSUnaided Prediction		Total
		Positive	Negative	
CDSD-aided Prediction	Positive	0.124	0.124	0.248
	Negative	0.299	0.453	0.752
	Total	0.423	0.577	1.00

**Table 9-6: Assumptions for Proportions of Predictions for Non-Adenomas (Specificity, Reference Standard Negative) with PCF-H190**

		CDSUnaided Prediction		Total
		Positive	Negative	
CDSD-aided Prediction	Positive	0.1415	0.1415	0.283
	Negative	0.2815	0.4355	0.717
	Total	0.423	0.577	1.00

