### 16.2 *Anticipated Benefits*

Subjects may receive no benefit from participation in this study. It is possible that in some cases, pathological results may be reconsidered based on CDSD prediction, in which case adenoma may be diagnosed when it otherwise might not have been.

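### Pathology is re-read only where it contradicts the CDSD-aided prediction, and the second reading becomes the truth; this biases both co-primary differences towards the device

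*Combined protocol and SAP*

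**What the plan says.** The rule stands in the ground-truth paragraphs of Section 5 (after Table 5-1) and again in Section 9.2.3: "In cases where the CDSD-aided endoscopist prediction and the pathology result differs, a recut and reanalysis of the tissue block will be conducted". In those cases "the second successful pathology reading will be recorded and used as the histopathological ground truth".

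Section 8.5 words it differently. It collects secondary results "in cases where a recut/re-analysis of specimen is requested by the endoscopist" and performed, which reads as a discretionary request, whereas Section 5 makes the recut automatic.

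On blinding, Section 5 says "The pathologist is blinded to the endoscopist predictions and CDSD prediction" and Section 5.2 says "Pathology will be blinded to all predictions". Neither makes separate provision for the second reading.

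Section 16.2 mentions as a possible benefit that "pathological results may be reconsidered based on CDSD prediction", so that an adenoma may be diagnosed that would otherwise have been missed.

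The decision rule in Section 9.1.1.3 is: "The null hypothesis is rejected if both lower bounds of the confidence intervals are greater than 0". The Revision History lists the handling of recuts among the changes made after FDA feedback, without giving that feedback.

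**The concern.** The co-primary comparison is paired: aided and unaided predictions on the same polyp are scored against one reference. The re-read depends on only one of the two. In the notation of Tables 9-1 and 9-2:

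- **Only the aided prediction is wrong (c, n).** All are recut. A reversal turns an unaided win into an aided win: c becomes p, and n becomes b. Each such move raises both differences.
- **Only the unaided prediction is wrong (b, p).** None is recut, so the opposite correction cannot happen.
- **Both are wrong (d, m).** All are recut, but a reversal (d to q, m to a) changes only the denominators. Each lowers one difference slightly and raises the other.

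The test under evaluation thus helps select its own reference standard. A more accurate second reading does not remove the problem, because errors are corrected only where they count against the aided prediction.

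Normal tissue is an obvious place for reversals. Section 9.1.1.3, assumption 11, says "The proportion of predictions with and without CDSD that will be assessed as normal tissue by pathology is estimated to be approximately 15" percent, or 0.15 x 1,918 = about 288 polyps. Section 5 scores normal mucosa as non-adenoma, and only those polyps called adenoma with aid are re-read.

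A recut ordered only on disagreement may also tell the pathologist that the aided prediction differed from the first reading. The supplied documents do not say who does the second reading or what the request discloses.

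At stake is the one-sided 2.5% error rate of the pivotal comparison, chiefly through sensitivity, where the planned effect is small.

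**Working it through.** **Reproducing the plan.** From Section 9.1.1.2, 2,400 x 0.85 x 0.52 x 1.81 = 1,920 polyps, against 1,918 stated. At 58% prevalence this gives N+ = 1,112 adenomas and N- = 806 non-adenomas. For sensitivity power, take the variance (b + c - diff^2)/N+ x [1 + (k - 1) x 0.05], with k = 1,112/80 = 13.9 adenomas per endoscopist-by-scope cluster. That is (0.1224 - 0.0384^2)/1,112 x 1.645, a standard error of 0.0134. Power is Phi(0.0384/0.0134 - 1.96), about 0.82. Specificity power is about 1.00, so joint power is about 0.82 against 80% stated. Sensitivity decides the trial.

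**Cells.** Averaging Tables 9-3 and 9-4, and Tables 9-5 and 9-6 (50% of subjects per scope, assumption 9):

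| | Proportions | Difference |
|---|---|---|
| Adenoma | a 0.8356, b 0.0804, c 0.0420, d 0.0420 | b - c = 3.84 points |
| Non-adenoma | m 0.13275, n 0.13275, p 0.29025, q 0.44425 | p - n = 15.75 points |

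Counts:
- aided-only errors, c + n = 47 + 107 = 154
- both wrong, d + m = 47 + 107 = 154
- total recut about 307 before rounding
- unaided-only errors, b + p = 89 + 234 = 323, none recut

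**Effect of reversals.** Let a fraction f of recut polyps reverse, with letters now denoting counts:

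- Sensitivity difference = [b - c + f(c + n)] / [N+ - f(c + d) + f(m + n)]
- Specificity difference = [p - n + f(n + c)] / [N- - f(m + n) + f(c + d)]

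On the planned cells at f = 5%, these become 4.5 and 16.8 points, against 3.84 and 15.75. If only d and m reverse, at 10%, the changes are -0.02 points (sensitivity) and +0.12 points (specificity). The denominator effects would outweigh the gain only if m reversed about 37 times as often as c and n (sensitivity), or d about 22 times as often (specificity).

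**No sensitivity benefit, specificity as planned.** Set a = 0.8164 and b = c = d = 0.0612, about 68 polyps each. The sensitivity formula becomes f(68 + 107)/(1,112 + 78f). At f = 10% this is 17.5/1,120 = 1.6 points. If only reversals towards adenoma occur (the direction Section 16.2 names), it is 107f/(1,112 + 214f).

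| Reversal rate f (assumed) | 2% | 5% | 10% | 20% |
|---|---|---|---|---|
| Spurious sensitivity gain, uniform (points) | 0.3 | 0.8 | 1.6 | 3.1 |
| Spurious gain, towards adenoma only (points) | 0.2 | 0.5 | 0.9 | 1.9 |

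**Reversals arising from first-reading error.** Let the first reading be wrong with probability e and the recut with probability e2. Truly aided-wrong polyps end mislabelled with probability e + (1 - e)e2, and aided-right polyps with probability e x e2. In the same null case:

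| First-reading error e (assumed) | 2% | 5% |
|---|---|---|
| Recuts that reverse | 8-10% | 19-22% |
| Spurious gain, accurate recut (e2 = 0) | 0.3 | 0.8 |
| Spurious gain, equally error-prone recut (e2 = e) | 0.6 | 1.5 |

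**False success.** The simulation used:
- 40 endoscopists with 60 consented subjects each (0.85 x 0.52 eligible) and 1 + Poisson(0.81) polyps per eligible subject
- Dirichlet cell probabilities with ICC 0.05 per scope and class
- polyp class drawn independently at 58%, because the plan's within-subject model is not in the supplied text
- 600 two-stage bootstrap draws and 2,400 null trials (Monte Carlo SE at most 0.6 points)

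Under the two-stage bootstrap, false success was 0.8% without recuts and 1.4%, 3.3% and 9.6% at 2%, 5% and 10% uniform reversal. Separate simulations gave 0.8-1.4% without recuts, 3.5% at 5% and about 12% at 10%. Under the error model it was 1.4-2.7% at e = 2% and 3.4-8.8% at e = 5%. With an endoscopist-level bootstrap it was 3.9% without recuts, 10% at 5% reversal and 25% at 10%.

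**The case against.** The asymmetry and its direction are hard to contest. The case against concerns size and remedy.

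- **Uniform reversal is a harsh model.** It scores every reversal as a new error, yet some reversals correct the first reading. When 8-10% of recuts reverse because of a 2% first-reading error, the spurious gain is 0.3-0.6 points, not the 1.6 of uniform reversal at 10%. If reversals go only towards adenoma, simulated false success is about 1.0% at 5% reversal and 3-4% at 10%. This stands: at low rates the 2.5% level may hold.
- **Absolute error rates depend on the bootstrap used.** Literal two-stage versions give 63-69% power rather than 80%, and an endoscopist-level version already gives 3.9% false success without recuts. This stands too. The rise with the reversal rate appears in both versions.
- **A safeguard may exist elsewhere.** Section 9.1.1.3 refers to a statistical analysis plan for a modelling detail that is not in the supplied text, and the FDA feedback is not visible. A first-reading analysis could sit there, but none appears in what was supplied.
- **The recut counts are upper bounds.** Sections 8.5 and 8.6 speak of requests, and the rule refers to a successful second reading. True, but fewer recuts under the same trigger remain one-sided.
- **Blinding is stated more than once.** Whether the second reading is compromised is a matter for clarification, and the bias does not depend on it.
- **The fix costs power.** It does, but the error it leaves is conservative rather than in favour of the device.

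**Conclusion.** The concern holds, and the rule should be changed before the primary analysis. As written, it shifts both co-primary differences towards the device in every scenario tried. The direction rests on the plan's own 2x2 tables and needs only that some recuts reverse, without the extreme concentration in cells d or m described above.

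The size rests on a reversal rate that none of the 11 sample-size assumptions supplies. Over the assumed ranges, a device with no sensitivity benefit would show a gain of 0.2 to 3.1 points, against a planned gain of 3.84. Control at one-sided 2.5% is not assured: it may hold at low reversal rates, and under the two-stage bootstrap it fails at 5% uniform reversal and above. Confidence in the magnitude is medium, since the within-subject model and the exact bootstrap are not visible.

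**What to change.** In Sections 5 and 9.2.3, make the first blinded pathology reading of every polyp the ground truth for the co-primary and secondary accuracy endpoints, and prespecify the recut-based result as a sensitivity analysis. Recuts can continue as written; only the reading that enters the primary analysis changes. Section 8.5 already collects both results. Align its request wording with the automatic rule, and state who does the second reading and what that person is told. Because recut handling was revised after FDA feedback, confirm the change against that feedback.

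The administrative cost is protocol and SAP wording. The statistical cost is that first-reading errors stay in the primary analysis. They are neutral if neither endpoint has a true effect; otherwise they shrink the differences. Power below is from 1,000 simulated trials (SE at most 1.6 points).

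| First-reading error (assumed) | 0% | 2% | 5% |
|---|---|---|---|
| Sensitivity difference (points) | 3.84 | 3.55 | 3.12 |
| Specificity difference (points) | 15.75 | 15.2 | 14.4 |
| Power, two-stage bootstrap | 63% | 53% | 40% |
| Power, endoscopist-level bootstrap | 80% | 72% | 61% |

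If the planning accuracies were already measured against a single reading, which the documents do not say, this loss is already in the plan. With no sensitivity benefit and specificity as planned, two-stage false success under the first-reading rule was 0.6% and 0.3% at 2% and 5% error.

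An alternative is to trigger the recut on disagreement with either prediction. That also removes the bias when neither endpoint has a true effect, but adds about 320 recuts (the 323 polyps in b and p).

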### 5.1 *Scale and Duration*

A minimum of 2,400 subjects will be enrolled in order to obtain predictions on at least 1,918 diminutive polyps. It is anticipated that the study will take up to 6 months to complete.

### 5.2 *Treatment Assignment*

For each participating endoscopist, consecutive subjects presenting for colonoscopy and meeting the pre-procedure entrance criteria will be consented and screened. Subjects meeting all the entrance criteria will be enrolled and undergo colonoscopy according to the standard of care with the added use of CDSD.

During the procedure, subjects found to meet any of the exclusion criteria will be excluded from the study. CDSD will be applied to all endoscopist-identified diminutive polyps in all subjects. Pathology will be blinded to all predictions. See Figure 5-1 for details.

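### The plan says pathology is blinded to all predictions, but the recut rule does not secure this for the second reading, which sets the truth for an expected 16% of polyps

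*Combined protocol and SAP*

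**What the plan says.** **Blinding.** Section 5, in the text after Table 5-1, says "The pathologist is blinded to the endoscopist predictions and CDSD prediction". Section 5.2 says "Pathology will be blinded to all predictions". Neither separates first from second readings. Section 5.3 relies on blinding for independent assessments and an unbiased comparison.

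**Recut rule.** Section 5, repeated in Section 9.2.3: "In cases where the CDSD-aided endoscopist prediction and the pathology result differs, a recut and reanalysis of the tissue block will be conducted". In those cases "the second successful pathology reading will be recorded and used as the histopathological ground truth".

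**Who acts, and on what.** Under Section 5 "the pathology report will be reviewed by the endoscopist". Section 8.5 lists the laboratory results to be collected, "including secondary lab results in cases where a recut/re-analysis of specimen is requested by the endoscopist". Section 8.6 mentions a requested re-evaluation but names no requester. Table 8-1 lists follow-up pathology as needed. Section 8.8 uses the sites' local laboratories. Section 16.2, on benefits, says that "pathological results may be reconsidered based on CDSD prediction".

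**Classes.** Every endoscopist prediction is adenoma or non-adenoma; Section 5 does not allow an unsure answer.

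**The concern.** A recut is ordered only on a mismatch, and there are two classes. If the first report says adenoma, a recut under this rule means that the aided call was non-adenoma, and the reverse. A reader who has the first report and knows the rule is therefore not blind to the aided call, whatever the form says. That reading then replaces the first one as truth for both co-primary endpoints.

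A reversal caused by such a cue goes in one direction: it turns an aided error into an aided success. Where the unaided call had been correct, it also turns that call into an error, so both the sensitivity and the specificity difference grow. The primary test asks whether the lower confidence bounds of these same differences exceed zero.

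The description of the request adds a smaller problem. Sections 5 and 9.2.3 make the recut automatic. Section 8.5 has it requested by the endoscopist, who knows all the calls and has read the report. Nothing in the plan governs how that request is worded.

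**Working it through.** **Inputs.** 2,400 subjects, 85% adequate preparation, 52% with a diminutive polyp, 1.81 polyps each, 58% adenomas (Section 9.1.1.2); 50% of subjects examined with each colonoscope (Section 9.1.1.3, assumption 9); cell proportions from Tables 9-3 to 9-6.

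**Step 1: the plan's polyp count.** 2,400 × 0.85 × 0.52 × 1.81 = 1,920, against 1,918 stated. It reproduces. With 1,918: adenomas 1,918 × 0.58 = 1,112.4; non-adenomas 1,918 × 0.42 = 805.6.

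**Step 2: polyps due for recut.**
- Adenomas called non-adenoma with aid: (0.073 + 0.095)/2 = 0.084; 1,112.4 × 0.084 = 93.4.
- Non-adenomas called adenoma with aid: (0.248 + 0.283)/2 = 0.2655; 805.6 × 0.2655 = 213.9.
- Total 307.3, and 307.3/1,918 = 16.0%.
- The rounded combined values of 92% and 73% agree: 0.58 × 0.08 + 0.42 × 0.27 = 0.1598.
- If all polyps were seen with one colonoscope: 0.58 × 0.073 + 0.42 × 0.248 = 14.7% (CF-HQ190, 281 polyps), or 0.58 × 0.095 + 0.42 × 0.283 = 17.4% (PCF-H190, 334 polyps).

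**Step 3: effect of a cue.** Cells are named as in Tables 9-1 and 9-2 and averaged over the two colonoscopes:
- Adenomas: b = 0.0804, c = 0.0420, d = 0.0420; as counts 89.44, 46.72, 46.72.
- Non-adenomas: m = 0.13275, n = 0.13275, p = 0.29025; as counts 106.94, 106.94, 233.81.

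Let a share r of the recuts move to the aided call. Then c moves to p, d to q, m to a and n to b. With counts:
- Sensitivity difference = [b − c + r(c + n)] / [1,112.4 + r(m + n − c − d)]
- Specificity difference = [p − n + r(c + n)] / [805.6 − r(m + n − c − d)]

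Here b − c = 42.7, p − n = 126.9, c + n = 153.7 and m + n − c − d = 120.4.

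| r (assumed) | Sensitivity difference | Specificity difference |
|---|---|---|
| 0 | 42.7/1,112.4 = 3.84 points | 126.9/805.6 = 15.75 points |
| 2% | 45.8/1,114.9 = 4.11 (+0.27) | 130.0/803.2 = 16.18 (+0.43) |
| 5% | 50.4/1,118.5 = 4.51 (+0.67) | 134.6/799.5 = 16.83 (+1.08) |
| 10% | 58.1/1,124.5 = 5.17 (+1.33) | 142.2/793.5 = 17.93 (+2.18) |

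At 5%, about 15 polyps change truth (0.05 × 307). The rise of 0.67 is 17% of the planned sensitivity gain (0.67/3.84).

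Half of the mismatches in these tables (cells d and m) are unaided errors too. Reversing them makes both calls correct and changes only the denominators. The calculation allows for this.

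**Step 4: the same cue with no true effect.** Set the discordant cells equal: b = c = (0.0804 + 0.0420)/2 = 0.0612 and n = p = (0.13275 + 0.29025)/2 = 0.2115. As counts, c = 68.1 and n = 170.4. At r = 5% both numerators become 0.05 × (68.1 + 170.4) = 11.9. The net move between classes is 0.05 × (277.3 − 114.8) = 8.1 polyps. The apparent gains are 11.9/1,120.6 = 1.1 points in sensitivity and 11.9/797.4 = 1.5 points in specificity, where the truth is zero.

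**The case against.** **The unblinding is inferred.** A reader might conclude that the second reading is unblinded, or that the request by itself discloses the aided call. The documents do not support that. Disclosure needs a second reader who knows both the recut rule and the first result, and the plan is silent on who reads the recut and what that reader receives. Section 8.8 says only that local laboratories are used. Section 5.2 also refers to Figure 5-1, which I could not see; a safeguard shown there would narrow the point. What stands is that an unqualified blinding statement has no described support for the second reading.

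**Section 8.5 need not give discretion.** A reader might infer that endoscopists choose which polyps to query, or that the plan contains three rival triggers. That goes too far. Section 8.5 is about which results are collected. An endoscopist who places an order that Section 5 makes mandatory satisfies both passages. Section 8.6 names no requester, and Section 16.2 describes a possible benefit, not a trigger. The wording still needs to be made consistent.

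**The reversal rate is not in the documents.** This is correct. The 2% to 10% range is an assumption, and the calculation starts from no genuine reversals. It shows direction and scale; it does not predict the bias.

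**An automatic request would not remove the cue.** This is also correct. A request sent only on mismatches still signals a mismatch, and a laboratory that wrote the first report can look it up. The fix therefore also narrows the blinding claim and adds an analysis on the first reading.

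**Conclusion.** The point holds as a gap between a stated property and the procedure. Blinding to all predictions is claimed for pathology as a whole, but the recut rule does not secure it for the reading that becomes the truth in an expected 16.0% of polyps (about 307 of 1,918; 14.7% to 17.4% by colonoscope). Section 16.2, which expects results to be reconsidered in the light of the device prediction, is hard to square with the claim.

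The 16% treats the planned accuracies as measured against the first reading and assumes that every mismatch is successfully recut. If those accuracies already reflect re-reading, the share recut would be higher.

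Any cue-induced bias favours the device on both endpoints. At the assumed 5% it adds 0.67 points to sensitivity and 1.08 to specificity. Whether such a cue will operate, and how strongly, cannot be settled from the documents.

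**What to change.** 1. **Blinding statements.** In Sections 5 and 5.2, limit them to the first reading and say that the second reading may be cued.
2. **Trigger.** In Section 8.5, replace the request by the endoscopist with one generated automatically from the database for every case that meets the Section 5 rule. Align Section 8.6, Table 8-1 and Section 16.2 with it.
3. **Request form.** Use a standard form with no prediction, no reason and no copy of the first report. State that this reduces the cue but does not remove it if the same laboratory reads the recut.
4. **Reporting.** Give the numbers of recuts due, done and reversed, by direction. Report both co-primary differences also with the first, blinded reading as truth for all polyps. Section 8.5 already collects both results. The gap between the two analyses mixes genuine corrections with any cue, so it shows their joint effect and does not isolate the cue.

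Cost: protocol wording, a small coordinator or data-management task, one added analysis, and a less favourable blinding claim. Sample size and procedure do not change.
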